## **4 Change to protocol specified analyses**

Not applicable.

## **5 Appendix**

### **5.1 Imputation rules**

#### **5.1.1 Study drug**

No imputation of the start date of infusion/injection or end date for infusion will be applied. Complete dates are required as per eCRF.

#### **5.1.2 AE, ConMeds and safety assessment date imputation**

**Table 5-1 Imputation of start dates (AE, CM) and assessments (LB, EG, VS)**

Missing Element	Rule
day, month, and year	

• No imputation will be done for completely missing dates

day, month	

• If available year = year of study treatment start date then

◦ If stop date contains a full date and stop date is earlier than study treatment start date then set start date = 01JanYYYY

◦ Else set start date = study treatment start date.

• If available year > year of study treatment start date then 01JanYYYY

• If available year < year of study treatment start date then 01JulYYYY

Missing Element	Rule
day	

• If available month and year = month and year of study treatment start date then

◦ If stop date contains a full date and stop date is earlier than study treatment start date then set start date= 01MONYYYY.

◦ Else set start date = study treatment start date.

• If available month and year > month and year of study treatment start date then 01MONYYYY

• If available month and year < month year of study treatment start date then 15MONYYYY

Any AEs and ConMeds with partial/missing dates will be displayed as such in the data listings.

Any AEs and ConMeds which are continuing as per data cut-off will be shown as 'ongoing' rather than the end date provided.

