### **2.1.3.9 Baseline**

For efficacy evaluations, the last non-missing assessment, including unscheduled assessments on or before the date of randomization is taken as “baseline” value or “baseline” assessment. In the context of baseline definition, the efficacy evaluations also include ECOG performance status. For biomarker, the last available data collected before the first dose of study treatment will be defined as “baseline”.

For safety evaluations, the last available assessment on or before the date of start of study treatment is taken as “baseline” assessment.

If subjects have no value as defined above, the baseline result will be missing.

In rare cases where multiple measurements meet the baseline definition, with no further flag or label that can identify the chronological order, then the following rule should be applied: If values are from central and local laboratories, the value from central assessment should be considered as baseline. If multiple values are from the same laboratory (local or central) or collected, then the worst value should be considered as baseline.

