### **2.1.3.10 On-treatment assessment/event and observation periods**

For adverse event reporting the overall observation period will be divided into three mutually exclusive segments:

1. ***pre-treatment period***: from day of subject’s informed consent to the day before first administration of study treatment
2. ***on-treatment period***: from date of first administration of study treatment to 130 days (approximately five terminal half-lives of canakinumab/pembrolizumab) after the date of last administration of study treatment
3. ***post-treatment period***: starting at day 131 after the date of last administration of study treatment

Safety summaries (tables, figures) and summaries of on-treatment death include only data from the on-treatment period with the exception of baseline data which will also be summarized where appropriate (e.g. change from baseline summaries). In addition, a separate summary for death including on treatment and post treatment deaths will be provided. In particular, summary tables for adverse events (AEs) will summarize only on-treatment events, with a start date during the on-treatment period (***treatment-emergent*** AEs).

An ***on-treatment assessment*** is defined as any assessment performed after the date of first administration of study treatment i.e. assessments performed in the following time interval (including the lower and upper limits): from date of first administration of study treatment +1 up to 130 days after the date of last administration of study treatment.

In case at time of the analysis, the date of last administration of study treatment is missing, on-treatment adverse event/assessment include any adverse event/assessment recorded in the database which occur after the start date of the study treatment.

However, all safety data (including those from the post-treatment period) will be listed and those collected during the pre-treatment and post-treatment period will be flagged.

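### SAP Table 5-1 dates some partly dated post-dose laboratory and vital-sign values to the day of first dose, which counts as baseline and not as on-treatment

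*SAP*

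**What the plan says.** SAP 5.1.2 has a single table of imputation rules, Table 5-1, headed "Imputation of start dates (AE, CM) and assessments (LB, EG, VS". It covers adverse events, concomitant medications, laboratory values, ECGs and vital signs.

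- **Day missing.** The branch opens with "If available month and year = month and year of study treatment start date then". Its one exception needs a full stop date earlier than treatment start. Otherwise: "Else set start date = study treatment start date".
- **Day and month missing.** The branch opens with "If available year = year of study treatment start date then" and ends in the same way.
- **Known month or year later than first dose.** The date goes to the first of that month or to 1 January of that year.
- **Known month or year earlier than first dose.** The date goes to the 15th of that month or to 1 July of that year.

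Two definitions decide what happens to the imputed date. For safety data, SAP 2.1.3.9 says "the last available assessment on or before the date of start of study treatment is taken as" baseline. SAP 2.1.3.10 gives the window for an on-treatment assessment as "from date of first administration of study treatment +1 up to 130 days after the date of last administration of study treatment". The adverse-event on-treatment period in that same section includes the day of first dose.

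**The concern.** Moving a vague date to the day of first dose is a conservative habit for adverse events: when in doubt, the event counts as treatment-emergent. Applied to an assessment, the same step does the reverse, because here the day of first dose belongs to baseline and lies outside the assessment window.

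An abnormal post-dose value dated this way is hidden. It may be shown as the patient's starting condition, or it may drop out of the on-treatment data. The outputs at stake are:

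- the laboratory shift tables and, on the natural reading, the worst post-baseline grade (SAP 2.7.3);
- the liver rows that depend on baseline transaminases or on multiples of baseline (SAP 2.7.3, liver function parameters);
- the notable weight, blood-pressure and pulse criteria, which need a change from baseline (SAP Table 2-4).

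**Working it through.** The plan states no figure to reproduce. The check follows the rules through and then asks how often the harmful branch is reached.

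**Following the rules.** A single laboratory or vital-sign assessment would not be expected to carry a stop date (my reading), so the stop-date exception does not apply.

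1. First dose 3 June 2021. A sample drawn on 24 June (Day 22) is recorded as June 2021. Month and year match, so the date becomes 3 June. That is on or before treatment start, so the value is a baseline candidate. It is before 4 June (start + 1), so it is not an on-treatment assessment.
2. Same patient. A sample drawn on 8 July is recorded as July 2021. The date becomes 1 July, and the value stays on-treatment.
3. In case 1, if the order on 3 June can be identified, the misdated value is the last one and becomes baseline. If it cannot, the tie rule in 2.1.3.9 takes the central value over a local one, or the worst value within one laboratory. The misdated value is then either baseline, or neither baseline nor on-treatment.

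**How often, given a partial date.** Assumptions, not in the documents: first dose equally likely on each day of a calendar year (366 days: seven months of 31 days, four of 30, one of 29), and last dose on Day 22. The window then runs from start + 1 to start + 21 + 130 = start + 151. Let *d* be the number of days after first dose.

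*Only the day missing.* The share moved to the start date is the sum over months of max(0, month length − *d*), divided by 366.

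- Day 22 (*d* = 21): (7×10 + 4×9 + 8)/366 = 114/366 = 31.1%. In a 365-day year: 113/365 = 31.0%.
- Days 2 to 22 (*d* = 1 to 21, mean 11): (366 − 12×11)/366 = 234/366 = 63.9%.
- About Day 36 (*d* = 35): 0%, since no month is that long.
- Full window (*d* = 1 to 151): each month contributes L(L − 1)/2, with L its length. The total is 7×465 + 4×435 + 406 = 5,401, and 5,401/(366×151) = 9.8%.

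*Day and month missing.* The share is (366 − *d*)/366.

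- Day 22: 345/366 = 94.3%.
- About Day 36: 331/366 = 90.4%.
- Full window (mean *d* = 76): 290/366 = 79.2%.

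All of these are conditional on the date being partial. The documents do not say how many will be.

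**The case against.** The strongest reply is that the effect is narrow and that other routes catch what matters. Much of it stands.

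- **Scope.** A reader might infer that every partial assessment date goes to the day of first dose. Table 5-1 does not do that. Later months and years stay on-treatment, and true pre-dose values from the same month are correctly kept in baseline.
- **ECG.** The table title names ECGs, so a reader might infer that ECG summaries lose values. SAP 2.7.4.1 plans only a listing, and the one scheduled ECG is pre-dose (protocol 8.4.2).
- **Direction.** It is tempting to say that the error always favours the drugs. It does not. A normal post-dose value that displaces a truly abnormal baseline makes later abnormalities look like larger shifts.
- **Worst grade.** It is also tempting to say that the value must vanish from the worst post-baseline grade. SAP 2.7.3 never defines post-baseline, and it takes all assessments up to 130 days after last dose. If another value is chosen as baseline, no text expressly bars the misdated one from that table. Exclusion is the natural reading but is not proven.
- **Other capture.** Scheduled laboratory work is central (protocol 8.4.1). Clinically significant abnormalities are recorded as adverse events (protocol 10.1.1), and missing values are queried (protocol 11.2). SAP 2.7.3 lists all laboratory data and all Grade 3 or 4 laboratory toxicities.

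The conflict itself remains. The sponsor named laboratory and vital-sign data in the table, so it foresaw partial dates there. SAP 5.1.1 requires complete dates only for study drug. Local results reach the eCRF when, for example, they drove a treatment decision or showed an adverse event that the central result missed (protocol 8.4.1); those are values a safety table should keep. A visit label would show that a value is post-dose, but the rule as written does not use it.

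**Conclusion.** The point holds for laboratory and vital-sign assessments whose known date part matches the month and year of first dose, or the year alone when the month is also missing. For these, following Table 5-1 gives a classification that conflicts with SAP 2.1.3.9 and 2.1.3.10. This is a stated rule that misclassifies, not a missing detail.

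The conditional shares above concentrate the problem in the first weeks after first dose, and they rest on the uniform-calendar and Day 22 assumptions. Absolute impact is unknown and probably small. Nothing in the primary analysis of major pathological response is touched. This is a minor correction, worth making because it is cheap and because hidden early toxicity is the likelier harm.

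**What to change.** Restrict Table 5-1 to adverse-event and concomitant-medication start dates. For laboratory and vital-sign assessments, state in the SAP:

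1. The date is not imputed. A partly dated value is classified as pre-dose or post-dose by its nominal visit.
2. Baseline is never selected from a partial or imputed date.
3. An unscheduled value with no visit label counts as post-baseline if the known part of its date allows a post-dose date, and it is flagged in the listing.

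The cost is a short SAP addition and a small derivation change. The downside is that an occasional unlabelled screening value may be counted as post-baseline, which is the conservative direction for safety.

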#### **5.1.2.1 Other imputations**

Not applicable

### **5.2 AEs coding/grading**

Adverse events are coded using the Medical dictionary for regulatory activities (MedDRA) terminology.

AEs will be assessed according to the Common Terminology Criteria for Adverse Events (CTCAE) version 5.0.

The CTCAE represents a comprehensive grading system for reporting the acute and late effects of cancer treatments. CTCAE grading is by definition a 5-point scale generally corresponding to mild, moderate, severe, life threatening, and death. This grading system inherently places a value on the importance of an event, although there is not necessarily proportionality among grades (a grade 2 is not necessarily twice as bad as a grade 1).

### **5.3 Laboratory parameters derivations**

Grade categorization of lab values will be assigned programmatically as per NCI Common Terminology Criteria for Adverse Events (CTCAE) version 5.0. The calculation of CTCAE grades will be based on the observed laboratory values only, clinical assessments will not be taken into account. The criteria to assign CTCAE grades are given in Novartis internal criteria for CTCAE grading of laboratory parameters. The latest available version of the document based on the underlying CTCAE version 5.0 at the time of analysis will be used. For laboratory tests where grades are not defined by CTCAE version 5.0, results will be graded by the low/normal/high (or other project-specific ranges, if more suitable) classifications based on laboratory normal ranges.

A severity grade of 0 will be assigned for all non-missing lab values not graded as 1 or higher. For laboratory tests that are graded for both low and high values, summaries will be done

separately and labelled by direction, e.g., sodium will be summarized as hyponatremia and hypernatremia.

### **Imputation Rules**

CTC grading for blood differentials is based on absolute values. However, this data may not be reported as absolute counts but rather as percentage of WBC.

If laboratory values are provided as ' $<X$ ' (i.e. below limit of detection) or ' $>X$ ', prior to conversion of laboratory values to SI unit, these numeric values are set to X.

The following rules will be applied to derive the WBC differential counts when only percentages are available for a xxx differential

$$\text{xxx count} = (\text{WBC count}) * (\text{xxx \%value} / 100)$$

Further derivation of laboratory parameters might be required for CTCAE grading. For instance, corrected calcium can be derived using the reported total calcium value and albumin at the same assessment using the following formula:

$$\text{Corrected Calcium (mg/dL)} = \text{Calcium (mg/dL)} - 0.8 [\text{Albumin (g/dL)} - 4]$$

In order to apply the above formula, albumin values in g/L will be converted to g/dL by multiplying by 0.1, calcium values in mmol/L will be converted to mg/dL by dividing by 0.2495. For calculation of laboratory CTC grades 0 and 1, the normal range for derived corrected calcium is set to the same limits (in mg/dL) as for calcium.

CTC grades for the derived absolute WBC differential counts (neutrophils, lymphocytes) and corrected calcium will be assigned as described above for grading.

## **5.4 Statistical models**

### **5.4.1 Primary analysis**

The estimate of the response rates (e.g., MPR, ORR, surgical feasibility rate) will be summarized in terms of percentage rates with 95% CIs. An exact binomial confidence interval (implemented using SAS procedure FREQ with EXACT statement for one-way tables) will be calculated ([Clopper and Pearson 1934](#)).

SAS procedure FREQ will be used to estimate the proportion of responders, along with the associated 95% two-sided exact binomial CI. The difference in MPR rate along with the two-sided exact 95% confidence interval based on Chan and Zhang (1999) can be obtained by using “exact” statement.

### **Calculation of posterior probability**

The criteria for proof of efficacy are:

- the mean of the posterior distribution of MPR is at least 30% and
- the posterior probability that the MPR is  $\geq 20\%$  is at least 90%

for canakinumab single agent arm and

- the mean of the posterior distribution of MPR is at least 45% and

- the posterior probability that the MPR is  $\geq 30\%$  is at least 90% for canakinumab and pembrolizumab combination arm.

Let  $p_1$  denote the MPR rate for canakinumab single agent and follow a beta prior distribution  $\text{Beta}(a_1, b_1)$ , where  $a_1 > 0, b_1 > 0$ . Let  $y_1$  out of  $n_1$  patients reach MPR in canakinumab single agent arm. Then the posterior distribution of  $p_1$  is  $\text{Beta}(a_1 + y_1, b_1 + n_1 - y_1)$  (Spiegelhalter et al. 2004). Similarly, for canakinumab and pembrolizumab combination arm, the posterior distribution of  $p_2$  is  $\text{Beta}(a_2 + y_2, b_2 + n_2 - y_2)$ .

A minimally informative unimodal Beta prior (Neuenschwander et al. 2008) will be used. For canakinumab single agent arm, the parameters will be chosen so that the mean of the prior distribution is equal to 0.3, which corresponds to  $\text{Beta}(3/7, 1)$ . For canakinumab in combination with pembrolizumab arm, the parameters will be chosen so that the median of the prior distribution is equal to 0.45, which corresponds to  $\text{Beta}(9/11, 1)$ .

The efficacy criteria will be assessed based on the actual number of patients enrolled. For example, if the total number of patients in canakinumab is 44, the first efficacy criterion requires that at least 14 patients who are MPR responders. In that case, the posterior distribution is  $\text{Beta}(3/7 + 14, 1 + 44 - 14)$  and the posterior probability  $P(\text{MPR rate} \geq 0.2) = 96.5\%$ .

